4.2 Rationale for dose/regimen and duration of treatment

Two secukinumab dosing regimens will be evaluated in this study:

- Secukinumab 300 mg s.c. every 4 weeks
- Secukinumab 300 mg s.c. every 2 weeks

Both dose regimens will start with an induction period consisting of 300 mg s.c. injections at Baseline, Weeks 1, 2, 3, and 4, followed by the maintenance treatment as described in [Section 3](#).

As clearly demonstrated in the development program for moderate to severe plaque psoriasis, it is expected that the induction period with weekly dosing during the first month will enable to quickly achieve effective drug concentrations and lead to a more rapid onset of clinical response.

Rationale for 300 mg s.c. every 4 weeks regimen

Secukinumab 300 mg s.c. with an initial weekly induction schedule up to 4 weeks followed by a s.c administration of every four weeks up to Week 48 is in line with the secukinumab Phase 3 registration program and the approved product labelling for moderate to severe plaque psoriasis. Initial information from case reports shows a positive clinical response to treatment in patients with HS treated with the psoriasis therapeutic dose ([Thorlacius et al 2017](#); [Schuch et al 2018](#)). The demonstrated positive benefit-risk of the 300 mg s.c. every 4 weeks regimen in psoriasis, another inflammatory dermatological disease, supported by case reports showing positive clinical effects in HS patients indicates the potential of this dose regimen to show a positive benefit-risk in HS and justifies further evaluation in this study.

Rationale for 300 mg s.c. every 2 weeks regimen

[figure not shown]
In addition to the psoriasis dose regimen, the second dose regimen will be evaluated to achieve a higher exposure for the following reasons:

- Higher body weights are expected for this population compared to the psoriasis population (approximately 10 kg heavier weight for HS population in clinical trials ([Kimball et al 2016](#))), thus potentially requiring higher doses to achieve adequate exposure. Secukinumab systemic exposure varies with body weight in an allometric relationship. For clearance, the allometric exponent was estimated to be close to 1; in other words, a doubling of body weight could lead to a nearly 2-fold increase in clearance and therefore reduced serum exposure ([Bruin et al 2017](#)). Therefore, evaluation of a dosing regimen with higher exposure than that resulting from the marketed regimen is appropriate in this heavier patient population.
- Higher local exposure than in psoriasis might be needed for this disease with deep inflammatory subcutaneous lesions.
- Clinical experience with adalimumab in HS supports a dosing regimen with higher exposure in HS than in psoriasis.

After the same induction period during the first month, considerably higher and more consistent systemic exposure can be achieved with a shortened dose interval (every 2 weeks) than can be reached with the 4 weeks interval ([Figure 4-1](#)).

Secukinumab 300 mg s.c. every 2 weeks has been tested in over 300 patients for at least 24 weeks in completed clinical studies in uveitis and psoriasis. A safety profile in line with that of secukinumab 300 mg s.c. every 4 weeks has been observed.

Figure 4-1 Predicted systemic exposure with 2 and 4 weeks dosing intervals during maintenance at the 300 mg dose level

[figure not shown]
4.3 Rationale for choice of control drugs (comparator/placebo)

Placebo will be used as the comparator. Use of placebo as a control arm will minimize the number of patients that need to be exposed to a treatment which is without confirmed benefit-risk in HS at this stage. Demonstration of efficacy using either a superiority or non-inferiority design against an active drug would require a large potentially unfeasible sample size in an indication with such low prevalence.

Due to the concerns of keeping patients with HS on placebo, the use of placebo is limited to a maximum of 16 weeks. In addition, the risks to patients who are randomized to placebo will be minimized by allowing some patients to enter on systemic antibiotic therapy and by allowing rescue therapy with systemic antibiotics for those patients presenting with a clinically relevant increase of inflammatory lesions during the placebo period.

After 16 weeks, all patients originally randomized to placebo will then be switched to active drug in a blinded manner.

4.4 Purpose and timing of interim analyses/design adaptations

A primary endpoint analysis will be performed after all subjects have completed the visit at Week 16.

At the end of the study, the final analysis of all data collected will be performed when all subjects have completed their last study visit. All subjects, investigators/site personnel will remain blinded until final database lock.

4.5 Risks and benefits

Secukinumab has demonstrated positive benefit-risk in the treatment of multiple chronic inflammatory indications including moderate to severe plaque psoriasis, ankylosing spondylitis, psoriatic arthritis. Based on the available evidence at the time of this protocol (see [Section 1.1](#) for further details), secukinumab has the potential to also show positive benefit-risk in reducing the extent of inflammation in patients with moderate to severe HS. Given the impact of these inflammatory lesions on the quality of life of patients with HS, a reduction in the number of such lesions could directly benefit patients.

Secukinumab therapy has a well-established and well-described safety profile based on extensive post-marketing experience and continued clinical trial patient exposure since its approval for the first indication of moderate to severe plaque psoriasis. Details of the risk and benefits are outlined in the current version of the Investigator's Brochure.

Observed risks at doses up to 300 mg s.c. every 4 weeks included infections, of which the most frequently reported were upper respiratory tract infections. Oral herpes, oral candidiasis and tinea pedis were also more frequently reported. Most of the infections were non-serious, mild to moderate in severity, clinically manageable and did not lead to treatment discontinuation. Neutropenia and hypersensitivity reactions are also risks observed with secukinumab. Cases of neutropenia were uncommon, generally mild to moderate, transient, did not lead to treatment discontinuation, and only a few cases were temporally associated with non-serious infections.

Secukinumab 300 mg s.c. every 2 weeks is not an approved dose regimen. It has been administered in 7 completed studies in approximately 460 patients with psoriasis and uveitis, with approximately 300 patients receiving continuous treatment for at least 24 weeks. This included over 200 patients with psoriasis. The safety profile observed in the available data is consistent with the known safety profile of secukinumab.

Treatment with multiple high doses of secukinumab (10 mg/kg and 30 mg/kg i.v.) has been administered to more than 2000 patients, with the majority receiving 3 doses of 10 mg/kg i.v. over 1 month and 38 patients receiving monthly doses for at least 6 months. Treatment with high doses (monthly exposure on chronic doses being approximately 2-fold higher compared to 300 mg s.c. every 2 weeks dose) was associated with a numerical increase in infections compared to placebo, mainly due to more reports of non-serious upper respiratory tract infections, but also a few more individual reports of non-serious local fungal infections such as oral or vulvovaginal candidiasis. Otherwise, the safety profile was consistent with the known safety profile of secukinumab with the approved doses.

The recently completed randomized, double-blind, multicenter study CAIN457A2324 (NCT03504852), evaluated the safety and efficacy of secukinumab 300 mg s.c. administered every 2 weeks (q2w) or every 4 weeks (q4w), in patients with psoriasis who weigh ≥ 90 kg. Study CAIN457A2324 showed that in psoriasis patients who weigh ≥ 90 kg, secukinumab 300 mg q2w demonstrates a better treatment effect. Whilst the efficacy data is not yet published at the time of release of protocol amendment 02, the analysis of the safety data did not demonstrate any new safety signals with the q2w regimen and showed an overall safety profile in line with what is already known.

The risk to subjects in this trial may be minimized by compliance with the eligibility criteria and study procedures, as well as close clinical monitoring, and periodic review of safety data by an independent DMC.

Based on all available data, and a positive benefit/risk ratio for the treatment of moderate to severe HS with secukinumab at doses 300 mg q4w and 300 mg q2w, it is appropriate to initiate study CAIN457M2302.

Additional information can be found in the IB for secukinumab.

5 Population

The study population will consist of a representative group of adult male and female patients (≥ 18 years old) with moderate to severe HS. The study originally aimed to randomize approximately 471 patients in approximately 132 study sites worldwide. To account for the disruptive impact of the COVID-19 pandemic on the conduct of the study since the release of protocol amendment 01, the number of randomized patients was increased to approximately 541 (15% increase from the original population of 471 patients). Up to 40% of the patients will be allowed to enter the study on treatment with stable dose of antibiotics. Patients who drop out after they have been randomized will not be replaced.

In case of a global health disruptive event, such as pandemic/epidemic impacting the conduct of the trial, patients or sites may not be able to perform the assessments as per protocol, leading to a potential increase in the number of missing measurements. If the latter should affect the power of tests and the precision of estimates for this study, the Sponsor may consider recruiting additional patients to restore the sample size and maintain the pre-defined statistical power.

5.1 Inclusion criteria

Patients eligible for inclusion in this study must meet **all** of the following criteria:

1. Written informed consent must be obtained before any assessment is performed.
2. Male and female patients ≥ 18 years of age.
3. Diagnosis of HS ≥ 1 year prior to baseline.
4. Patients with moderate to severe HS defined as:
 - A total of at least 5 inflammatory lesions, i.e. abscesses and/or inflammatory nodules AND
 - Inflammatory lesions should affect at least 2 distinct anatomic areas
5. Patients agree to daily use of topical over-the-counter antiseptics on the areas affected by HS lesions while on study treatment.

5.2 Exclusion criteria

Patients meeting any of the following criteria are not eligible for inclusion in this study.

1. Total fistulae count ≥ 20 at baseline.
2. Any other active skin disease or condition that may interfere with assessment of HS.
3. Active ongoing inflammatory diseases other than HS that require treatment with prohibited medications (see [Table 6-2](#)).
4. Underlying conditions (including, but not limited to metabolic, hematologic, renal, hepatic, pulmonary, neurologic, endocrine, cardiac, infectious or gastrointestinal such as inflammatory bowel disease) which in the opinion of the investigator significantly immunocompromises the patient and/or places the patient at unacceptable risk for receiving an immunomodulatory therapy.
5. Current severe progressive or uncontrolled diseases which renders the patient unsuitable for the trial or puts the patient at increased risk, including any medical or psychiatric condition which, in the Investigator's opinion, would preclude the participant from adhering to the protocol or completing the study per protocol.
6. Use or planned use of prohibited treatment. Washout periods detailed in the protocol have to be adhered to (see [Table 6-2](#)).
7. For patients enrolling in the non-antibiotic strata: use of systemic antibiotics for the treatment of HS within 28 days before baseline.
For patients enrolling in the antibiotic strata: patients enter the study under concomitant treatment with systemic antibiotics (as per protocol) on a stable dose (defined as a dose or dose regimen that has not changed in the previous 28 days before baseline and is considered unlikely to change at least for the first 16 weeks during the study).
8. History of hypersensitivity to any of the study drug constituents.
9. Previous exposure to secukinumab (AIN457) or any other biologic drug directly targeting IL-17 A/F or the IL-17 receptor.
10. History of chronic or recurrent systemic infections or active systemic infections during the last two weeks (exception: common cold) prior to randomization.
11. Evidence of tuberculosis infection as defined by a positive QuantiFERON® TB-Gold test (QFT) at screening. Patients with a positive or indeterminate QFT test may participate in the study if a full tuberculosis work-up (according to local practice/guidelines) completed within 12 weeks prior to randomization, establishes conclusively that the patient has no

evidence of active tuberculosis. Subjects positive for latent TB per work-up may be randomized to the trial if sufficient treatment has been initiated according to local routine clinical practice and was completed at least four weeks before randomization.

12. Medical history record of infection with human immunodeficiency virus (HIV), hepatitis B or C prior to randomization, except for hepatitis C successfully treated and cured.
13. History of lymphoproliferative disease or any known malignancy or history of malignancy of any organ system treated or untreated within the past 5 years, regardless of whether there is evidence of local recurrence or metastases (except for skin Bowen's disease, or basal cell carcinoma or actinic keratoses that have been treated with no evidence of recurrence in the past 12 weeks; carcinoma in situ of the cervix or non-invasive malignant colon polyps that have been removed).
14. History or evidence of ongoing alcohol or drug abuse, which in the opinion of the investigator will prevent the patient from adhering to the protocol and completing the study.
15. Pregnant or lactating women.

16. Women of childbearing potential, defined as all women physiologically capable of becoming pregnant, unless they are using methods of contraception during the entire study or longer if required by locally approved prescribing information (e.g. in European Union (EU) 20 weeks).

Contraception methods include:

- Total abstinence, when this is in line with the preferred and usual lifestyle of the patient. Periodic abstinence (e.g. calendar, ovulation, symptothermal, post-ovulation methods) and withdrawal are not acceptable methods of contraception.
- Female sterilization (have had surgical bilateral oophorectomy with or without hysterectomy), total hysterectomy or bilateral tubal ligation at least six weeks before taking study treatment. In case of oophorectomy alone, only when the reproductive status of the woman has been confirmed by follow-up hormone level assessment.
- Male sterilization (at least 6 months prior to screening). The vasectomized male partner should be the sole partner for that patient.
- Barrier methods of contraception: Condom or Occlusive cap (diaphragm or cervical/vault caps). For United Kingdom: with spermicidal foam/gel/film/cream/vaginal suppository.
- Use of oral (estrogen and progesterone), injected or implanted hormonal methods of contraception or other forms of hormonal contraception that have comparable efficacy (failure rate <1%), for example hormone vaginal ring or transdermal hormone contraception or placement of an intrauterine device (IUD) or intrauterine system (IUS).

In case of use of oral contraception, women should have been stable on the same pill for a minimum of 3 months before taking study treatment.

In case local regulations deviate from the contraception methods listed above, local regulations apply and will be described in the informed consent form (ICF).

Note: Women are considered post-menopausal and not of childbearing potential if they have had 12 months of natural (spontaneous) amenorrhea with an appropriate clinical profile (e.g. age appropriate, history of vasomotor symptoms) or have had surgical bilateral oophorectomy (with or without hysterectomy), total hysterectomy or bilateral tubal ligation

at least six weeks prior to enrollment. In the case of oophorectomy alone, only when the reproductive status of the woman has been confirmed by follow-up hormone level assessment is she considered not of childbearing potential.

No additional exclusions may be applied by the investigator, in order to ensure that the study population will be representative of all eligible patients.

6 Treatment

6.1 Study treatment

6.1.1 Investigational and control drugs

Table 6-1 Investigational and control drug

Investigational/ Control Drug (Name and Strength)	Pharmaceutical Dosage Form	Route of Administration	Blinding/volume	Sponsor (global or local)
Secukinumab 300 mg	Solution for injection	Subcutaneous Use	Double blinded subject packs; 2 ml pre-filled syringe	Sponsor (global)
Placebo	Solution for injection	Subcutaneous Use	Double blinded subject packs; 2 ml pre-filled syringe	Sponsor (global)

Novartis will supply the investigational therapy as follows:

- Secukinumab 300 mg solution for sub-cutaneous injection in a 2 ml pre-filled syringe
- Placebo solution for sub-cutaneous injection in a 2 ml pre-filled syringe

Each placebo pre-filled syringe contains a mixture of inactive excipients, matching the composition and the appearance of the secukinumab 300 mg dose.

Secukinumab and the secukinumab matching placebo will be labeled as “AIN457 300 mg / Placebo” (2 ml) to keep the blind. Subjects will be initially instructed about injections by site staff. They will also receive instructions on how to self-inject using the pre-filled syringe.

6.1.2 Additional study treatments

No additional treatment beyond investigational drug and control drug are included in this trial. Subjects are requested to use over-the-counter antiseptics according to eligibility criteria, [Section 6.2.1](#) and [Section 6.2.2](#). For rescue medication, see [Section 6.2.3](#).

6.1.3 Treatment arms/group

At Baseline/Randomization visit, all eligible subjects will be randomized via Interactive Response Technology (IRT) in a 1:1:0.5:0.5 ratio to one of the following 4 treatment groups:

- **Secukinumab 300 mg every 2 weeks group:** subjects will receive a loading dose of secukinumab 300 mg once weekly for four weeks (at Randomization, Weeks 1, 2, 3 and 4), followed by secukinumab 300 mg every two weeks, starting at Week 6 and up to Week

50. These subjects will receive two additional placebo injections at Weeks 17 and 19 to maintain the treatment blind during the re-induction.

• **Secukinumab 300 mg every 4 weeks group:** subjects will receive secukinumab 300 mg once weekly for four weeks (at Randomization, Weeks 1, 2, 3 and 4), followed by secukinumab 300 mg every four weeks, starting at Week 8 and up to Week 48. In order to maintain the treatment blind, subjects in this group will also receive a placebo injection every 4 weeks starting at Week 6, until Week 50. These subjects will receive three additional placebo injections at Weeks 17, 18 and 19 to maintain the treatment blind during the re-induction.

• **Placebo group to secukinumab 300 mg every 2 weeks:** subjects will receive placebo once weekly for four weeks (at Randomization, Weeks 1, 2, 3 and 4), followed by placebo every two weeks, starting at Week 6 and up to Week 14. At Week 16, subjects will be switched from Placebo to Secukinumab 300 mg every 2 weeks. The subjects will receive secukinumab 300 mg once weekly for four weeks (Weeks 16, 17, 18, 19 and 20), followed by secukinumab 300 mg every two weeks, starting at Week 22 and until Week 50.

• **Placebo group to secukinumab 300 mg every 4 weeks:** subjects will receive placebo once weekly for four weeks (at Randomization, Weeks 1, 2, 3 and 4), followed by placebo every two weeks, starting at Week 6 and up to Week 14. At Week 16, subjects will be switched from Placebo to Secukinumab 300 mg every 4 weeks. The subjects will receive secukinumab 300 mg once weekly for four weeks (Weeks 16, 17, 18, 19 and 20), followed by secukinumab 300 mg every four weeks, starting at Week 24 and up to Week 48. To maintain the treatment blind, subjects will receive placebo alternating with secukinumab starting at Week 22 and up to Week 50.

See [Figure 3-1](#) for graphical representation of type of injection per treatment group and visit.

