Subjects who complete Treatment Period 1 will enter Treatment Period 2.

Treatment Period 2 (Week 16 post-dose to Week 52)

Treatment Period 2 is defined as the time from Week 16 (post-dose) through Week 52. From Week 16, all patients will receive secukinumab.

The Week 16 dose is the first dose of Treatment Period 2.

Subjects who were randomized to either of the two secukinumab regimens will continue on the same dose regimen. Subjects who were randomized to one of the two 'Placebo to secukinumab' regimens will receive either secukinumab 300 mg every 2 weeks or secukinumab 300 mg every 4 weeks.

At Week 16, all subjects will receive a re-induction consisting of a single s.c. injection of blinded study drug (active drug or placebo) once a week for four weeks, at Week 16, 17, 18, 19 and 20. Thereafter, all subjects will receive study drug injections every 2 weeks, either

secukinumab alternating with placebo every 2 weeks (secukinumab 300 mg every 4 weeks arm) or secukinumab every 2 weeks (secukinumab 300 mg every 2 weeks arm) until Week 50.

Home administrations (**H**) of study drug are scheduled at Weeks 22, 26, 30, 34, 38, 42, 46 and 50.

The planned end of Treatment Period 2 visit (EOT 2) will be performed at Week 52. At this visit, the site should call Interactive Response Technology (IRT) after performing the scheduled study assessments to record the completion of treatment period by subject(s). For subjects rolling over to the extension study, Week 52 will be the end of study visit; for subjects continuing to the Post-Treatment Follow-Up, the visit at Week 60 will be the end of study visit.

Subjects who discontinue study treatment prematurely for any reason other than withdrawal of informed consent before Week 52 should not be considered as discontinued from the study. Subjects should continue attending site visits for the study assessments. Subjects who are unwilling to continue attending further study visits after discontinuing the study drug, should attend the end of study visit. The End of Treatment visit (EOT 1 for discontinuation during Treatment Period 1 and EOT 2 for discontinuation during Treatment Period 2) which should be performed two weeks (where possible) after their last dose of study drug. After the EOT visit, subjects should enter the post-treatment Follow-Up period.

[figure not shown]

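### Read literally, Protocol Section 6.1.3 gives the secukinumab q4w arm two placebo injections at Week 18, in conflict with the single weekly injection in Section 3 and the identical schedule in Section 6.4

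*Protocol*

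**What the plan says.** Section 6.1.3 of the Protocol describes the secukinumab q4w arm in three steps after the weekly loading phase.

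- Active drug: "followed by secukinumab 300 mg every four weeks, starting at Week 8 and up to Week 48".
- Regular blinding placebo: "subjects in this group will also receive a placebo injection every 4 weeks starting at Week 6, until Week 50".
- Extra placebo at re-induction: "These subjects will receive three additional placebo injections at Weeks 17, 18 and 19".

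For the secukinumab q2w arm, whose regular injections also fall on Week 18, the matching sentence names only two weeks: "These subjects will receive two additional placebo injections at Weeks 17 and 19".

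Section 3 (Treatment Period 2) sets one rule for everyone from Week 16: "all subjects will receive a re-induction consisting of a single s.c. injection of blinded study drug (active drug or placebo) once a week", at Weeks 16, 17, 18, 19 and 20. Section 6.4 lists the schedule of administration among the features that are identical across treatments and so conceal their identity. Section 6.1.3 refers the reader to Figure 3-1 for the injection type by group and visit. That figure is not visible in the copy reviewed.

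**The concern.** The placebo injections in 6.1.3 exist only to protect the blind, so their number has to match across arms at every visit. A regular series that includes Week 18, followed by extra injections that also include Week 18, gives one arm a second syringe at that visit.

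Week 18 is a scheduled visit in Table 8-1 and is not among the home-administration weeks. Site staff who hold the protocol and see two kits assigned could work out that the patient is in the q4w arm, even though the syringes look alike. Section 6.4 requires patients, site staff and assessors to stay blinded to individual allocation until the study ends. Physician lesion counts and patient-reported outcomes continue to Week 52, and it is these later assessments that would be exposed.

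**Working it through.** No document gives a total number of injections per arm, so there is no stated total to reproduce. The check enumerates each arm from 6.1.3 and compares it with the time points in Section 3.

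**Time points implied by Section 3, one injection each**

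- Baseline and Weeks 1, 2, 3, 4: 5
- Weeks 6 to 50 every 2 weeks: (50 − 6)/2 + 1 = 23
- Weeks 17 and 19, the weeks of re-induction not on the 2-weekly grid: 2
- Total: 5 + 23 + 2 = 30

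**Arms as written in 6.1.3**

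| Arm | Active | Placebo | Total | Weeks 16, 17, 18, 19, 20 |
|---|---|---|---|---|
| q2w | 5 + 23 = 28 | 2 (Weeks 17, 19) | 30 | 1, 1, 1, 1, 1 |
| q4w | 5 + 11 = 16 | 12 + 3 = 15 | 31 | 1, 1, 2, 1, 1 |
| Placebo to q2w | 5 + 15 = 20 | 5 + 5 = 10 | 30 | 1, 1, 1, 1, 1 |
| Placebo to q4w | 5 + 7 = 12 | 5 + 5 + 8 = 18 | 30 | 1, 1, 1, 1, 1 |

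**Terms for the q4w arm**

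- Active, Weeks 8 to 48 every 4 weeks: (48 − 8)/4 + 1 = 11. This includes Weeks 16 and 20 but not 18.
- Regular placebo, Weeks 6 to 50 every 4 weeks: (50 − 6)/4 + 1 = 12, namely Weeks 6, 10, 14, 18, 22, 26, 30, 34, 38, 42, 46 and 50. This includes Week 18.
- Extra placebo: 3 (Weeks 17, 18, 19).

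**Terms for the placebo-start arms**

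- Placebo before the switch: 5 loading injections plus Weeks 6, 8, 10, 12 and 14, so 5 + 5 = 10.
- Placebo to q2w, active: 5 at Weeks 16 to 20, then Weeks 22 to 50 every 2 weeks, (50 − 22)/2 + 1 = 15.
- Placebo to q4w: active 5 at Weeks 16 to 20, then Weeks 24 to 48 every 4 weeks, (48 − 24)/4 + 1 = 7. Placebo at Weeks 22 to 50 every 4 weeks, (50 − 22)/4 + 1 = 8, following the statement that "subjects will receive placebo alternating with secukinumab starting at Week 22 and up to Week 50".

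**Gaps left by the regular series.** Set against the 30 time points, the regular q2w series leaves Weeks 17 and 19 uncovered, and 6.1.3 states two extra injections there: it reproduces. The regular q4w series, active plus placebo, also leaves only Weeks 17 and 19 uncovered, but 6.1.3 states three: it does not reproduce. Week 18 in the q4w arm is the only duplicate in any arm.

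**The case against.** The strongest reply is that Weeks 16 to 20 form a self-contained re-induction block, with alternation of active and placebo resuming afterwards, as Section 3 can be read. Within that block active drug falls at Weeks 16, 18 and 20 for q2w and at Weeks 16 and 20 for q4w. The remaining slots are 17 and 19 for q2w, and 17, 18 and 19 for q4w. Those are exactly the two lists in 6.1.3. On this reading the sentences list the placebo slots within re-induction, and the q4w total is 16 + (12 − 1) + 3 = 30.

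This is a plausible account of the intent, and the q2w sentence fits either reading because that arm has no regular placebo series. It does not fit the q4w paragraph as worded. There the three injections are called additional, directly after a placebo series that runs to Week 50 with no exception for re-induction. The reading also needs the arm's active series to run through Weeks 16 and 20 while the parallel placebo series is silently suspended at Week 18.

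Other parts of the objection stand:

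- Sites do not know the arm and dispense what the IRT assigns (Sections 6.3.2 and 6.7). A second syringe would appear only if the IRT had been built on the literal q4w text, and nothing in the documents shows that it was.
- Figure 3-1 may already show one injection at Week 18.
- Assessments precede dosing (Sections 6.7.2 and 8), so the Week 18 lesion count itself would be taken before any second syringe was used.
- The figure of about 180 is the number randomized to the arm (Section 3), not the number still on treatment at Week 18, which the documents do not give.

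**Conclusion.** The text of 6.1.3 is inconsistent as written, by one placebo injection at one visit in one arm (31 against 30). It contradicts Sections 3 and 6.4. The point is minor, but this is an operative dosing and blinding instruction, so it should be settled. The count assumes that the regular placebo series is taken as stated, without an unstated gap at Week 18.

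A reader might infer more than this, and the documents do not support it:

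- *That the confirmatory results are at risk.* The primary and secondary endpoints are assessed up to Week 16, before Week 18. Later efficacy analyses are exploratory, with no formal confirmatory tests planned (Protocol 12.6, SAP 2.13).
- *That the arm receives a different amount of active drug.* Both Week 18 injections would be placebo.
- *That the blind was in fact broken.* That depends on the IRT build and on Figure 3-1, neither of which can be seen here.
- *That the dose tables in SAP 2.5.1 would be wrong.* That section summarises the number of secukinumab and placebo doses by group. It uses no planned number as a target or denominator, so the wording of 6.1.3 cannot make it wrong.

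**What to change.** Reconcile the two placebo sentences for the q4w arm in Section 6.1.3 with Section 3, Figure 3-1 and the IRT kit specification, so that the number of Week 18 injections in that arm is stated once and agrees everywhere. Which schedule is intended is for the sponsor to confirm; none is proposed here.

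The cost is about one sentence of protocol wording and one check of the IRT specification. Section 14.1 requires a written amendment for any change of text, so the wording can go into the next amendment, while the IRT check can be done at once. For patients already past Week 18, the kit assignments recorded in the IRT (Section 6.7.2) show how many syringes were issued at that visit. If any q4w patient was assigned two, the study report should say so when it describes blinding in Treatment Period 2. No change to the SAP is needed.
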